Study duration: We will recruit for a year and a half. Patients will be followed for 1 year. We estimate 4 years total.

Primary outcome measure: *Pain* as measured by using the arithmetic mean of the four pain severity items on the patient-reported Brief Pain Inventory assessment (BPI) 2-weeks following the patient's injury.

Secondary outcome measures: *Length of stay* will be determined by recording the admission date versus discharge date for the patient's index hospitalization. *Time to first mobilization (bed to chair)* will be determined using the physical therapy notes during the patient's index hospitalization and is defined as days post-injury and days post-operative treatment (if applicable) to time of first mobilization (bed to chair). *Narcotic use* will be determined by cross-referencing the patient's medical record during the index hospitalization and follow-up clinic appointments with patient-reported usage. *Work productivity and impairment* will be determined using the modified WPAI:SHP questionnaire. *Health related quality of life* will be measured using the VR-12 questionnaire. *Pelvic function* will be measured using the Majeed Pelvic Score.

Statistical analysis: We are interested in estimating the causal effect of operative treatment versus non-operative treatment in lateral compression type pelvic fracture patients. For all our

analyses, we will report estimates of the causal effects, standard errors, and confidence intervals. We will also report the results of tests of null hypothesis of no causal effect.

KEY ROLES

Safety Monitor- [name] will be responsible for overseeing patient safety for the study. [name] will review the enrollment numbers and medical compliance annually for the duration of the study.

Coordinating Center Principle & Sub-Investigators- [name] [name] (PI) and the sub-investigators will be responsible for developing a detailed study protocol, providing oversight on study progress and act to correct deficiencies in the conduct of the study. The PI and sub-investigators will also draft the main publications related to the study, and assist with patient consent.

Site Principle & Sub-Investigators- The site PI and sub-investigators will be responsible for oversight on local study progress. The site PI and sub-investigators will also contribute to the main publications related to the study, and assist with patient consent.

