Our primary hypothesis is that the operative treatment group will have lower VAS pain scores compared to the non-operative treatment group both during their hospital stay and in the short-term outpatient follow-up.

Based on the results of a pilot study, we expect pain scores in the non-operative group to have a mean of 5.7 and a standard deviation of 2.3. Assuming a 20% reduction in pain scores, 130 patients (65 per arm) are required to have an 80% chance of detecting, as significant at the 5% level, a decrease in the primary outcome measure from 5.7 in the control group to 4.56 in the experimental group. This is our primary outcome and the study will be powered for this variable.

Primary data analysis will involve direct comparison of the change in value of the reported pain scores at the time points listed below. We will be powered to detect a 20% reduction in pain. Secondary analysis will compare the value of narcotics administered at the distinct time periods. Tertiary analysis will be comparing the time (in days) to mobilization with physical therapy. The previous retrospective pilot study incorporated a propensity factor, generated from well documented sources of pain. As this is a prospectively randomized trial, we do not anticipate needing to accommodate for matching.

RANDOMIZATION

Eligible patients will be randomized in equal proportions to one of the two treatment groups: 1) operative treatment of the lateral compression type fracture, 2) non-operative treatment of the lateral compression type fracture. Allocation will be concealed using a centralized 24-hour computerized randomization system, www.randomize.net, that will allow Internet based allocation. The treatment allocation will be stratified on the following prognostic factors to ensure balance between the intervention groups: 1) patient intubation status at time of enrollment, 2) patient prescription pain medication usage during the month prior to injury.

DATA MANAGEMENT

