**Pelvis RCT: Impact of Surgery on Pain in Lateral Compression Type Pelvic Fractures**

**NCT: 02625766**

**December 28, 2020**

### Statistical Analysis

[figure not shown]
The primary analyses were based on the intent-to-treat principle. The primary analysis for pain and secondary analysis for functional outcome estimated the difference in the average treatment effect based on a longitudinal assessment within the initial 12-weeks after the fracture. This approach uses each patient's multiple outcome assessments to compare the average pain and function experienced over the 12-week period between the treatment groups. For these analyses, we used a Bayesian hierarchical model that applied a prior probability of no treatment difference based on the conflicting evidence in the prior literature [3-6]. This is akin to an initial assumption that there is "no difference" in pain or functional outcome between the treatment groups. In addition to estimating the average treatment effect, we calculated the posterior probability (meaning conditioning the prior distribution on the data at hand) of treatment benefit with operative treatment under various minimally clinical important difference (MCID) thresholds. The models included a dummy variable for each patient as a random intercept, an autoregressive correlation structure, and adjusted for whether the treatment was randomly assigned, the patient's pre-injury narcotic use, and a time-varying covariate that measured narcotic use at each time point. Multivariable linear regression was used to analyze the treatment effect on hospital length of stay and time to mobilization. Outcome data were missing in 16% of the sample at 2-weeks, and 14% of the sample at 6-weeks and 12-weeks, and was therefore imputed using multiple imputation for the final models [16]. To assess possible effect measure modification based on the initial degree of displacement, we stratified the sample to create two subgroups, patients with  $\geq 5$ mm of displacement and patients with  $< 5$ mm of displacement. We then calculated the average effect of operative treatment on pain in each of the subgroups. In addition, we compared the average treatment effect of operative fixation on pain with posterior-only fixation compared to operative fixation with anterior and posterior fixation. Additional sensitivity analyses recalculated the pain and function outcomes to separately compare the treatment effects between patients enrolled in the randomized cohort and the observational cohort. The analyses were performed using R Version 3.6.1 (Vienna, Austria) with the packages *lme4*, *rstan*, *brms*, and *mice*.

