
We took two critical steps to understand the potential for biased treatment estimates from pooling the results from the randomized and non-randomized participants. First, we performed sensitivity analyses to separately examine the results for the randomized and non-randomized cohorts. These analyses suggested similar (or even larger) estimated treatment benefits from surgery within the RCT data. Second, we included willingness to be randomized as a potentially confounding variable in our final analysis models, despite there being no evidence that it affected treatment.

[figure not shown]
The ability to assess the probability of different magnitudes of treatment benefit is a unique characteristic of Bayesian data analysis, and is not possible with traditional non-Bayesian statistical hypothesis testing. Despite this inherent difference in statistical principles, it should be noted that the average treatment benefits reported from our Bayesian analysis are nearly identical to the results obtained using traditional multilevel linear regression models (results not reported).

Additional results from the described analyses, that were not included in the main article, are provided below.

[figure not shown]
**Posterior probability of reduced pain.** Posterior probability of reduced pain with operative treatment within 12 weeks of injury.

[figure not shown]
**Mean pain stratified between randomized and nonrandomized patients.** The mean Brief Pain Inventory scores and 95% credible intervals within the initial 12-weeks of injury for minimally displaced complete lateral compression pelvis fracture patients. The patients are stratified based on their study type (randomized trial versus observation) and treatment type (operative versus nonoperative treatment). The pain scores are adjusted for the study type, prior narcotic use, and narcotic use at each time point.

**Posterior probability of improved function.** Posterior probability of improved function, measured with the Majeed score, with operative treatment within 12 weeks of injury.

**Mean function stratified between randomized and nonrandomized patients.** The mean Majeed scores and 95% credible intervals within the initial 12-weeks of injury for minimally displaced complete lateral compression pelvis fracture patients. The patients are stratified based on their study type (randomized trial versus observation) and treatment type (operative versus nonoperative treatment).

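### The protocol's 5% test and 80% power belong to a 2-week comparison that the SAP does not present; the SAP gives Bayesian output with no decision rule and leaves the traditional results unreported

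*SAP*

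**What the plan says.** **Protocol, Protocol Summary.** The primary outcome is the mean of the four BPI severity items 2 weeks after injury. The statistical analysis paragraph says that for all analyses "we will report estimates of the causal effects, standard errors, and confidence intervals", and adds: "We will also report the results of tests of null hypothesis of no causal effect".

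**Protocol, Data Analysis.** On pilot data, "we expect pain scores in the non-operative group to have a mean of 5.7 and a standard deviation of 2.3". The target effect is "a decrease in the primary outcome measure from 5.7 in the control group to 4.56 in the experimental group". The planned size of 65 per arm, 130 in all, is meant to give 80% power to find this difference "as significant at the 5% level". Whether the test is one- or two-sided is not stated.

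**SAP, Statistical Analysis.** The primary pain analysis is a Bayesian hierarchical model of average pain over the first 12 weeks. Randomised and non-randomised participants are pooled, with an adjustment for whether treatment was randomly assigned. Besides the average effect, the SAP calculates posterior probabilities of benefit "under various minimally clinical important difference (MCID) thresholds". On the non-Bayesian models, it says that the average treatment benefits were "nearly identical to the results obtained using traditional multilevel linear regression models (results not reported". The text contains no significance level, no p-value, no designated threshold and no probability cut-off for concluding benefit. It does not mention a 2-week test.

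**The concern.** A significance level and a power figure describe one procedure: a given outcome, time point, population and rejection rule. The protocol supplies all of these in outline. The SAP changes the time point (2 weeks to a 12-week average), the population (randomised to pooled) and the form of inference (a test to a set of posterior probabilities). It then leaves out the only results that could have been read as a conventional test.

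At stake is whether a reader can say what error rate stands behind a claim of benefit. The protocol's 5% and 80% cannot be carried over to the 12-week pooled model, and the SAP offers no rule whose error rate could be worked out in their place. The commitment to report tests and confidence intervals is also unmet within the SAP.

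**Working it through.** **1. Reproduce the design.** Inputs from the protocol's Data Analysis section: means 5.7 and 4.56, SD 2.3, 5% level, 80% power, 65 per arm.

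- Difference: 5.7 − 4.56 = 1.14, which is 20% of 5.7.
- Normal approximation, two-sided: n = 2 × (1.960 + 0.842)² × 2.3² / 1.14² = 63.9, so 64 per arm.
- Two-sample t-test, two-sided: 64.9, so 65 per arm, as planned.
- One-sided (normal approximation): 51 per arm, 102 in total, which does not match.
- Power at 65 per arm, two-sided: 80.7% (normal), 80.1% (t-test).

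The planned size therefore rests on a two-sided 5% test. The two-sidedness is inferred from the number.

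**2. Set the two plans side by side.**

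| | Protocol | SAP |
|---|---|---|
| Outcome | BPI severity at 2 weeks | BPI pain averaged over 12 weeks |
| Patients | Randomised 1:1 | Randomised and observational, pooled |
| Inference | Test at 5%, confidence interval | Posterior probabilities, credible intervals |
| Rule for benefit | Significance at 5% | None stated |
| Traditional results | Promised | Fitted, not reported |

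The SD of 2.3 and the difference of 1.14 were set for the left-hand column. They do not give the power of the right-hand one.

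**3. Show what an unstated rule leaves open.** The SAP does not specify its prior or model closely enough to compute its error rates. As illustration only, assume a flat prior, SD 2.3, 65 per arm and a single 2-week comparison. Then SE = 2.3 × √(2/65) = 0.403. Take the rule: declare benefit if Pr(reduction > c) ≥ g. This means declaring benefit when the estimate exceeds c + z_g × SE, so

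- false-positive rate at zero effect = 1 − Φ((c + z_g × SE)/SE)
- power at 1.14 = 1 − Φ((c + z_g × SE − 1.14)/SE)

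| c | g | False positives | Power |
|---|---|---|---|
| 0 | 0.975 | 2.5% | 80.7% |
| 0 | 0.95 | 5% | 88.1% |
| 0 | 0.80 | 20% | 97.6% |
| 0.5 | 0.80 | 1.9% | 77.2% |
| 1.0 | 0.80 | 0.05% | 31.0% |

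The first row is the design test in the direction of benefit. The others are rules that the SAP's wording would equally allow.

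**4. Check the one table of thresholds available.** The SAP's displacement table gives, for < 5 mm, a mean difference of 0.9 (95% CrI 0.1 to 1.8). A normal approximation has SD = 1.7/3.92 = 0.434 and gives 98%, 82%, 41%, 8% and 1% at > 0, 0.5, 1.0, 1.5 and 2.0, matching every printed figure. For ≥ 5 mm, SD = 2.6/3.92 = 0.663. The fit is looser there (85% against the printed 88% at > 1.5; 62% against 65% at > 2.0). The table is coherent. It concerns subgroups over 12 weeks and is not the primary analysis.

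**The case against.** The strongest reply is that the protocol frames its aim as estimating a causal effect, and that a Bayesian estimation report needs no binary cut-off. Credible intervals are given for the displacement subgroups, and under a flat prior a 97.5% probability of any benefit is the planned test in one direction. This stands so far: choosing a Bayesian model is not in itself a fault. It does not meet the separate promise to report tests and confidence intervals. The SAP never says that an interval excluding zero is its criterion. Its prior is described only as one of no difference, so the equivalence is approximate.

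Second, the tests may be in the main article, which the SAP supplements, or in figures not available here. That cannot be checked, so the point is limited to the SAP's text.

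Third, the SAP analyses the randomised cohort separately and says the estimated benefits there were similar or larger. This is reassuring about direction, but it concerns the SAP's own 12-week outcomes and supplies no test.

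Three stronger readings are tempting and are not supported:

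- *That the same data support opposite conclusions.* In the < 5 mm column, 98% at > 0 and 8% at > 1.5 are points on one posterior: some benefit is likely, a large one is not. The thresholds are printed together, so selective emphasis would be visible.
- *That 1.14 points should have been the threshold.* The approximation in step 4 would put the probability of exceeding it at about 29% (< 5 mm) and 94–95% (≥ 5 mm). But 1.14 is a 2-week powering difference, never called a minimal clinically important difference, and these are 12-week subgroup effects. Its absence from a subgroup table says nothing about what the primary figure displays.
- *That unfavourable tests were withheld.* The SAP says the average benefits agreed. It is silent on standard errors and p-values, and silence is not evidence of a null result.

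**Conclusion.** The point holds in this form. The protocol's 5% level and 80% power attach to a two-sided comparison of 2-week BPI severity between randomised arms. The SAP presents no such comparison, states no decision rule for what it does present, and leaves the traditional results out.

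The effect on the trial's conclusion cannot be sized, because neither the 2-week estimate nor the primary posterior is available in the text. The rates in step 3 show only how widely error rates vary across unstated rules; they rest on a flat prior, SD 2.3 and 65 per arm.

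A reader might infer that reporting the missing test costs no analysis because the models exist. The documents do not support this. The traditional models are described only as agreeing with the SAP's own analysis, and nothing shows that a 2-week, randomised-only model was fitted.

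One assumption concerns the outcome. Other parts of the protocol speak of VAS scores and several time points. The outcome is taken here from the Protocol Summary, which names instrument, score and time together.

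**What to change.** 1. Report the protocol's primary comparison: BPI severity at 2 weeks, randomised cohort, by assigned arm, with estimate, standard error, 95% confidence interval and two-sided p-value. State the number randomised per arm and how the missing 2-week outcomes (16% of the sample) are handled.
2. Report the same quantities from the traditional multilevel models already fitted.
3. Label the posterior probabilities at all thresholds as descriptive. If the probability at 1.14 points is added, label it post hoc and do not use it as a success rule. The SAP, dated December 2020, already contains results, so any cut-off set now would be chosen after them.

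The cost is one short additional analysis and one table. The 2-week randomised-only estimate will be less precise than the pooled 12-week one. With SD 2.3 and a full 65 randomised per arm, the 95% interval would be about ±0.79 (1.96 × 0.403). If 16% were missing in each arm (65 × 0.84 = 54.6 per arm), complete cases would give SE = 2.3 × √(2/54.6) = 0.440, an interval of about ±0.86, and power at 1.14 of about 74%. Fewer randomised patients would widen it further; the documents do not give the number randomised.
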